#### **9.4 Exploratory Analyses**

At the end of the study, study investigators may wish to explore other relationships between the treatment and outcomes and/or covariates. Because the number of subgroup analyses could be large and may be a combination of non-inferiority and superiority hypotheses, all subgroup analyses will be conducted using a two-tailed significance level of 0.01. The Publication Committee of the SVI Trial will review proof of concept papers with analysis plan submitted by any investigators wishing to do so before any further analyses are conducted by the study statisticians.

### **10. SAFETY ANALYSES**

All adverse events and serious adverse events will be summarized by AE code in terms of frequency of the event, number of subjects having the event, severity, expectedness (anticipated/unanticipated) and relatedness to the study treatment. In addition to the continual monitoring of adverse events by the safety monitor and DSMB and the planned statistical monitoring for safety (described in the SVI Safety Plan), final analyses of specified safety outcomes will be conducted. The proportion of subjects experiencing serious adverse events will be compared between the two treatment arms using Fisher's exact test. All tests for safety will use a two-tailed significance level of 0.05. See the Safety Monitoring Plan for further details about safety monitoring.

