3.2 Rationale

The SVI trial is a natural next step in the advancement of our understanding of PEP prevention by answering a critically important clinical question: *can we replace an invasive and costly preventive intervention with a safe and inexpensive one?*

Potential impact of replacing PSP with rectal indomethacin prophylaxis:

Research focusing on whether PSP remains necessary in the era of indomethacin prophylaxis is critical because replacing prophylactic stent placement by indomethacin mono-prevention in clinical practice has the following major potential advantages:

1. Improving clinical outcomes by avoiding the phenomenon of attempted but failed PSP, which is associated with a high rate of PEP by causing pancreatic orifice injury but providing no ductal decompression.^{11,12} As mentioned, PSP is generally (but not universally) successful and effective in expert hands, however there are no data evaluating the success rates and effectiveness of PSP in real-life practice – it is possible that this phenomenon of failed PSP is occurring more frequently than has been reported in clinical trials from expert research centers.
2. Improving clinical outcomes by avoiding the significant non-pancreatitis complications induced by PSP. Complications such as stent migration and duct perforation occur in up to 4% of cases.⁴ Rare complications may also occur during follow-up upper endoscopy to retrieve retained stents.
3. Improving clinical outcomes because indomethacin alone may actually be more effective for preventing PEP than any strategy that employs PSP. As mentioned above, a *post hoc* analysis of our indomethacin RCT revealed that, after adjusting for underlying imbalances in the prevalence of risk factors for PEP between groups, subjects who received indomethacin alone (7.1% PEP rate) appeared to be at lower risk for PEP than subjects who received no prophylaxis (23% PEP rate), those who received PSP alone (16% PEP rate), and those who received the combination of indomethacin and PSP (9.5% PEP rate).¹⁶ Indomethacin alone may be more effective than any strategy involving PSP because it avoids manipulation of the pancreatic orifice and instrumentation of the pancreatic duct, interventions that are necessary to place a pancreatic stent but are also known to contribute to pancreatitis.

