## 3. OUTCOME VARIABLES

### 3.1 Primary Efficacy Outcome

The primary outcome is a binary outcome variable measuring the post-ERCP pancreatitis event for each subject. Post-ERCP pancreatitis (PEP) is defined as: 1) New or increased pain in the upper abdomen and 2) amylase or lipase  $\geq 3x$  the upper limit of normal 24 hours after the procedure and 3) hospitalization (or prolongation of existing hospitalization) for at least 2 days (at least the night of ERCP & following night). These events must occur within 2 days of randomization in order to be considered PEP.

Using these consensus guidelines as a diagnostic framework, three adjudicators will independently assess for the development of PEP based on review of medical records and site-provided AE narrative for each study subject hospitalized within 2 days after the ERCP. PEP will be declared if at least 2 of the 3 adjudicators determine that a subject met all three components of the consensus diagnosis.

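### The single formal safety test in SAP 10 counts any SAE without excluding PEP, so it would have little power to show the non-pancreatitis stent harms

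*SAP*

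**What the plan says.** SAP 10 states: "The proportion of subjects experiencing serious adverse events will be compared between the two treatment arms". The method is Fisher's exact test, and "All tests for safety will use a two-tailed significance level of 0.05". SAP 5.3 puts all randomized subjects in the safety sample. No other between-arm safety test is named, and PEP is not taken out of the count. The rest of SAP 10 is descriptive ("All adverse events and serious adverse events will be summarized by AE code", with severity, expectedness and relatedness) or points elsewhere ("planned statistical monitoring for safety (described in the SVI Safety Plan), final analyses of specified safety outcomes will be conducted").

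SAP 3.1 and Protocol 11.1 require, for a primary-endpoint event, "hospitalization (or prolongation of existing hospitalization) for at least 2 days". Adjudicators work partly from an AE narrative supplied by the site. Neither document gives criteria for an SAE; Protocol 1.1 expands the abbreviation as severe, whereas SAP 10 writes serious.

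Protocol 3.2 lists among the potential advantages of dropping the stent: "Improving clinical outcomes by avoiding the significant non-pancreatitis complications induced by PSP". It adds: "Complications such as stent migration and duct perforation occur in up to 4% of cases". SAP 2 repeats the avoidance of stent complications when it explains why a non-inferiority design was chosen.

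**The concern.** Under the usual hospitalization criterion a primary-endpoint PEP is also an SAE. The any-SAE proportion then consists mostly of PEP, which already has its own analysis. The other side of the trade-off, harm from the stent that is not pancreatitis, becomes a small increment on a large shared count.

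Two things follow. With equal PEP rates, the PEP events add variance and hide the increment. If PEP is somewhat more frequent on indomethacin alone, the two differences have opposite signs and partly cancel. Either way, a non-significant SAE test could be read as no difference in safety when it says little about stent harm. That harm is one of the stated reasons for accepting up to 5 points more PEP, yet SAP 10 plans no pre-specified estimate with an interval for it.

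**Working it through.** **The plan's own figures.** The safety comparison has no stated power or expected SAE rate. The nearest stated figures reproduce:
- Non-inferiority power at 650 per arm, Φ(0.05/√(2p(1−p)/650) − 1.96): 86.1% at p = 9.7% (SAP 4.3: about 85%) and 76.4% at p = 13% (SAP 4.3: 76%).
- At 1090 per arm, 12.0% against 9.7%: SE = √(0.120×0.880/1090 + 0.097×0.903/1090) = 0.0133, giving a 95% CI of −0.3% to 4.9%, as in SAP 4.1.

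**Inputs from the documents.** 1090 per arm; two-sided Fisher test at 0.05; PEP 9.7%, with 13% as the high scenario (SAP 4.3); indomethacin-alone PEP 12.0% as the ceiling (SAP 4.1); stent complications up to 4% (Protocol 3.2, seriousness not stated).

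**Assumptions (not in the documents).** Background non-PEP SAEs b = 2% or 5% in both arms. Serious stent harm h = 1% to 4%, in the combination arm only and added to b. PEP independent of other SAEs.

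**Formulas.** PEP excluded: b + h against b. PEP counted: 1 − (1 − PEP)(1 − b − h) against 1 − (1 − PEP)(1 − b).

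**One case by hand (b = 2%, h = 4%), normal approximation**
- PEP excluded: 6.0% against 2.0%. SE = √((0.06×0.94 + 0.02×0.98)/1090) = 0.00835; 0.04/0.00835 = 4.79; power Φ(4.79 − 1.96) = 99.8%.
- PEP counted, 9.7% in both arms: 1 − 0.903×0.94 = 15.12% against 1 − 0.903×0.98 = 11.51%. SE = 0.01453; 0.0361/0.01453 = 2.48; power Φ(0.52) = 70%.
- PEP counted, 12.0% on indomethacin alone: 15.12% against 1 − 0.880×0.98 = 13.76%. SE = 0.01505; 0.0136/0.01505 = 0.90; power Φ(−1.06) = 14%.

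**Exact power of the two-sided Fisher test**, counting only rejections that show the combination arm worse:

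| b | h | PEP excluded | Counted, 9.7% both | Counted, 13% both | Counted, 12.0% v 9.7% |
|---|---|---|---|---|---|
| 2% | 4% | 99.8% | 68% | 57% | 13% |
| 2% | 3% | 97% | 45% | 36% | 4% |
| 2% | 2% | 76% | 23% | 18% | 1% |
| 2% | 1% | 27% | 9% | 7% | <1% |
| 5% | 4% | 95% | 61% | 52% | 13% |
| 5% | 3% | 79% | 39% | 33% | 5% |
| 5% | 2% | 47% | 20% | 17% | 1% |
| 5% | 1% | 15% | 8% | 7% | <1% |

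Combining h and b as independent events instead of adding them lowers these figures by at most about 4 points.

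**How much of the count is PEP.** Across the equal-PEP scenarios the share of subjects with any SAE who have PEP runs from 0.097/0.1783 = 54% (combination arm, b = 5%, h = 4%) to 0.13/0.1474 = 88% (indomethacin alone, b = 2%, PEP 13%).

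**The last column.** The SAP's 12.0% is a ceiling on the observed rate; here it is used as a true rate. With those true rates the trial would claim non-inferiority about half the time: Φ((0.05 − 0.023)/0.0133 − 1.96) = Φ(0.07) = 53%.

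**The case against.** Several points on the other side stand.

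- **PEP as an SAE is inferred.** No section says that PEP is reported as an SAE. The hospitalization requirement and the AE narrative make it very probable, but a reader should not take it as written.
- **The Safety Monitoring Plan is not among the documents.** SAP 10 and Protocol 13.5 both refer to it. It may exclude PEP or compare stent events, so the statement that there is one formal test applies to the SAP text only.
- **The events are visible elsewhere.** AE-code summaries separate pancreatitis from perforation or migration, and the closed reports give safety data by arm (SAP 1 and 4.3). A reader might infer that stent harm would be hidden from the DSMB or from the final report. The documents do not support that. What is missing is a pre-specified grouping and an interval.
- **Full cancellation would not pass unnoticed.** A reader might infer that equal SAE totals could conceal a real PEP excess. With b = 2%, h = 4% and a 4-point excess (13.7% against 9.7%), the any-SAE rates are nearly equal, about 15.4% on indomethacin alone against 15.1%, and the test rejects about 5% of the time. But the PEP difference would then be 4.0% with a 95% CI of 1.3% to 6.7%, so non-inferiority would fail openly in the primary analysis.
- **The cited 4% is an upper figure, with seriousness not stated.** At 1% serious harm, power is low either way: about 15% to 27% with PEP excluded, 7% to 9% with it counted at equal rates. Protocol 8.2.6 also allows stents that are placed for access and then removed in the indomethacin-alone arm, which would shrink the contrast further.
- **Capture is limited.** Stent X-ray follow-up begins 1 to 4 weeks after ERCP and is left to the treating endoscopist (Protocol 8.2.8), while the last study contact is at 30 days (8.3.2). Some retrieval events may fall outside follow-up, so a formal test on them is not justified.

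Non-pancreatitis stent harm is also not a listed objective (Protocol 2.1 and 2.2). It is, however, part of the stated rationale in both documents.

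**Conclusion.** The point holds for the formal test and no further. SAP 10 should not leave open whether PEP counts in its one between-arm safety comparison. If PEP counts, as is very probable, power to show serious stent harm of 2% to 4% falls from about 47%–99.8% to about 17%–68% at equal PEP rates, and to about 1%–13% at 12.0% against 9.7%. The masking therefore does not need a PEP excess large enough to defeat non-inferiority. These figures rest on assumed background SAE rates, on the cited complications being serious at 2% to 4%, and on independence of PEP from other SAEs. The direction is the same in every scenario computed, but the gain from excluding PEP is small if serious stent harm is about 1%. The primary analysis and the descriptive safety reporting are not affected.

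**What to change.** In SAP 10:

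1. State that adjudicated PEP is excluded from the formal SAE comparison. Report the risk difference with 95% CI for subjects with at least one non-PEP SAE.
2. Keep the all-SAE proportion as a descriptive total by arm.
3. Tabulate by arm, descriptively, a group of stent and duct events listed in advance and limited to those captured within follow-up (for example migration and duct perforation).
4. If the Safety Monitoring Plan already does any of this, cite the place instead.

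The cost is SAP wording plus one additional comparison and table. Trial conduct, sample size and the primary analysis do not change.
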